8. STATISTICS AND DATA ANALYSIS

The primary endpoint is babies' truncal skin surface temperature variation; also termed core or central temperature. This is expected to fluctuate but remain within normal temperature limits (36.5 to 37.5 degrees Celsius). Variations from this endpoint will be analysed and compared statistically between the two arms of the study.

Thirty-six completed datasets are required for the analysis to be valid. A complete subject dataset will be deemed acceptable if 19 of the 24, once-hourly temperature observations have been recorded for each incubator type (*i.e.* 79% compliance). This degree of compliance was considered acceptable for analysis because it is still greater than the routine standard for this type of incubator care for clinically stable infants of 30 weeks GA or greater, which is often every three hours. Although data analysis will be largely descriptive, the performance of the mOm incubator will be statistically quantified by assessment of the fluctuations of babies' temperatures during each 24-hour period. It is expected that these babies' temperatures will fluctuate by around one degree Celsius, and this is normal. Thus, analysis will explore whether fluctuations for each baby keep within this bound. A 95% confidence interval will be calculated around the mean of these fluctuations within each baby for each of the two incubators. Data from 36 babies would allow such a confidence interval to be calculated to within plus or minus 0.33 of a degree if the actual mean fluctuations are around one degree (*i.e.* as normally expected) and assuming a two-sided confidence interval.

Each patient will serve as their own control. The order of incubator type used for each of the two consecutive 24-hour periods of incubator care, and therefore which study arm the subject is recruited to, will be assigned randomly. A Microsoft Excel random number generation system will be used to generate random numbers with which the arm of the study which the subject is to enter will be assigned. Each assignment will be placed in an envelope attached to each CRF already numbered with a continuous series subject number.

Baseline demographic factors of the study subjects will be summarised. For continuous variables, such as weight, the mean, standard deviation, median and range will be presented. For categorical variables, such as gender, the proportion of subjects in each category will be presented.

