All data will be analysed based on intention-to-treat. Statistical analysis will focus on babies' temperature fluctuations whilst in each of the two incubators. Graphical displays of these, as well as summary statistics such as the variance of temperature throughout the two 24-hour periods will be presented. A 95% confidence interval for the size of these temperature fluctuations for each incubator type will be calculated and this measure will be used to consider whether the mOm incubator works as well as the standard one in maintaining temperature control. Secondary outcome measures will be presented similarly.

Questionnaire data will be summarised to assess usability and acceptability of the mOm incubator to the clinical research team (staff).

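### The conclusion that mOm works as well rests on a fluctuation measure that reads as within-period spread; a steady shift to colder or warmer does not change it, and no between-incubator estimate of temperature level is specified

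*Combined protocol and SAP*

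**What the plan says.** Section 8 makes variation in truncal skin temperature the primary endpoint and expects readings to stay between 36.5 and 37.5 °C. It then describes how performance is judged:

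- Each baby's temperature, it expects, "will fluctuate by around one degree Celsius, and this is normal". Taking that figure as a limit on the swing, "analysis will explore whether fluctuations for each baby keep within this bound".
- The estimate is specified separately by incubator: "A 95% confidence interval will be calculated around the mean of these fluctuations within each baby for each of the two incubators".
- Besides graphs, "summary statistics such as the variance of temperature throughout the two 24-hour periods will be presented". Variance is the only example statistic named.
- On the interval for fluctuation size in each incubator type: "this measure will be used to consider whether the mOm incubator works as well as the standard one in maintaining temperature control".

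Two other sentences in Section 8 bear on level. After the temperature limits comes "Variations from this endpoint will be analysed and compared statistically between the two arms of the study", with no statistic or model. For other outcomes, which include hourly truncal temperature (4.2.2) and axillary temperature (4.2.1): "Secondary outcome measures will be presented similarly".

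Section 2 states the hypothesis as temperature stability, and Section 4.1 makes stable core skin temperature the primary outcome. The primary objective (3.1) is a comparison of the level of thermal care in the two incubators.

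**The concern.** An incubator can fail in two ways: it can let the baby's temperature swing, or it can hold it steadily at the wrong level. The measure tied to the conclusion appears to address only the first. The limits in Section 8 concern the second, yet no analysis is set against them.

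Spread belongs in the conclusion, because stability is the hypothesis and the primary outcome. But followed as written, the trial could report that mOm works as well because spread is equal, while babies run somewhat colder or warmer in it. The one sentence that promises a statistical comparison names the two arms. Section 5 defines these as the two orders of treatment, each containing both incubators, so taken literally it does not compare the devices.

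**Working it through.** **The plan's own figure.** Section 8 gives a precision of ±0.33 °C with 36 babies and states no SD. With an assumed SD of 1 °C, 1.960 × 1/√36 = 0.327, which rounds to 0.33. The figure reproduces, but it is the precision of fluctuation size in one incubator and says nothing about a difference in level.

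**Invariance.** For readings x₁ to x₂₄ and any constant c:

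- max(x + c) − min(x + c) = max(x) − min(x)
- Var(x + c) = Var(x), and so for the SD

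This is exact and needs no assumption about SDs.

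**What a shift does to readings outside the limits (illustration).** Assumed: mean 37.0 °C in the standard incubator, within-baby SD 0.2, between-baby SD 0.15. Total SD = √(0.2² + 0.15²) = 0.25. Share outside = Φ((36.5 − μ)/0.25) + 1 − Φ((37.5 − μ)/0.25). The range is simulated with 24 hourly readings per period and lag-1 autocorrelation 0.3.

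| Mean μ (°C) | Outside limits, total SD 0.25 | Total SD 0.18 to 0.32 | Mean 24-h range (°C) |
|---|---|---|---|
| 37.0 | 4.6% | 0.6% to 11.8% | 0.76 |
| 36.9 | 6.3% | 1.4% to 13.6% | 0.76 |
| 36.8 | 11.8% | 4.8% to 18.9% | 0.76 |
| 36.7 | 21.3% | 13.4% to 27.2% | 0.76 |

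The total SDs of 0.18 and 0.32 come from within-baby SD 0.15 with between-baby SD 0.1, and from 0.25 with 0.2. With autocorrelation 0.6 the range is 0.71 at every mean.

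**Set to the plan's one degree.** With within-baby SD 0.26 and independent readings, the simulated mean range is 1.01 °C. Total SD = √(0.26² + 0.15²) = 0.30. Readings outside the limits are then 9.6% at 37.0 and Φ(−1.00) + Φ(−2.33) = 15.9% + 1.0% = 16.9% at 36.8, with the range again unchanged.

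**Simulated trials.** 36 babies, mOm 0.2 °C colder, 4,000 trials per setting; within-baby SD 0.15 to 0.25, autocorrelation 0.3 or 0.6, baby-by-period SD 0 or 0.15.

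| Quantity | Result |
|---|---|
| The two incubators' 95% intervals for mean range overlap | 99.3% to 99.7% of trials (no shift, SD 0.2: 99.4% to 99.6%) |
| 95% interval for paired difference in mean temperature excludes zero | 99.5% to 100% |
| Half-width of that interval | 0.019 to 0.085 °C |
| 95% interval for paired difference in share outside limits excludes zero | 37% to 88% |
| Half-width of that interval | 4.3 to 8.2 percentage points |

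If paired differences in mean temperature vary more, with assumed SDs of 0.2, 0.3 or 0.5 °C, the half-width is 0.07, 0.10 or 0.17 °C.

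**The case against.** The strongest reply is that fluctuation is undefined and need not mean spread. The sentence "Variations from this endpoint will be analysed and compared statistically between the two arms of the study" follows directly after the limits and could mean departures from them, which would be sensitive to level. The one-degree bound also equals the width of the limits. That reading is possible, but no such measure is defined, and the rest of Section 8 speaks of size, within each baby, during each 24-hour period, with variance as the example.

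Second, level of thermal care in Section 3.1 may only mean standard of care. That is fair, but the point stands on the plan's own temperature limits and its reference to temperature control.

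Third, level is partly visible in graphs, in the secondary temperatures and in hypothermia and hyperthermia recorded as adverse events (7.1), and the analysis is described as largely descriptive. True, but presenting secondary outcomes similarly may mean fluctuation again, and none of these is tied to the conclusion.

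Fourth, the illustration has limits, and these stand:

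- The SDs are assumed. Overlap of intervals is only a yardstick, since the plan states no decision rule.
- With a baby-by-period SD of 0.15, the change at 0.2 °C is from 8.6% to 16.0% rather than 5% to 12%.
- Clinical evaluation of temperature concerns (2.1.2) makes large sustained shifts less likely.
- A shift that occurs inside the measured period does widen the range. If the first three readings stay at the old level, the mean range rises from 0.76 to 0.80 °C for a 0.2 °C shift and to 1.02 °C for a 0.5 °C shift.

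**Conclusion.** The concern holds. On the natural reading of Section 8, the only measure tied to the conclusion does not change under a steady shift in temperature, and no between-incubator estimate of level, or of readings outside 36.5 to 37.5 °C, is specified. The invariance is exact once fluctuation means range, SD or variance. The size of the consequence depends on assumed SDs: for a 0.2 °C shift from 37.0 to 36.8, readings outside the limits rise from 1% to 5% at the low end and from 12% to 19% at the high end, with no change in spread. This should be fixed. The gap is in the specified analysis and its link to the conclusion, not in data collection.

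**What to change.** In Section 8:

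1. Define fluctuation, for example as the 24-hour range or the within-baby SD of hourly truncal temperature.
2. Base the conclusion on that measure together with two within-baby differences, mOm minus standard, each with a 95% confidence interval: mean truncal temperature, and the proportion of hourly readings outside 36.5 to 37.5 °C.
3. Replace the comparison between the two arms with one between the two incubators.
4. Report how many babies exceed 1 °C of fluctuation in each incubator, which answers the plan's own question about each baby.

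Hourly truncal temperatures are already collected and each baby is its own control, so the cost is wording and a few table rows. The downside is that the conclusion then rests on more than one measure, and the share outside the limits is the less precise of the two differences. These are estimates with intervals: an interval that includes zero does not by itself show that the incubators are comparable.

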2. RATIONALE

The mOm incubator fulfils the need to provide incubator care for babies requiring thermoregulation where standard incubators may not be available, such as in low to medium income countries.

This study aims to compare the ability of the mOm incubator to provide an adequate thermoregulated environment when used in a clinical setting using a prospective, multi-centre, randomised, cross-over study design to provide a direct comparison with standard incubators. It is hoped that the results of this study and the introduction of the mOm incubator could help to improve the survival rates of preterm babies born in places where access to expensive standard incubators is limited or not available.

The hypothesis is that the mOm incubator will perform as well as a standard incubator for routinely maintaining temperature stability in the baby.

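### The similarity claim for mOm rests on two separate confidence intervals, with no within-baby difference estimated and no limit set on it

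*Combined protocol and SAP*

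**What the plan says.** Section 2 (Rationale) sets the claim: "The hypothesis is that the mOm incubator will perform as well as a standard incubator for routinely maintaining temperature stability in the baby".

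Section 8 (Statistics and data analysis) says how the claim will be judged: "A 95% confidence interval for the size of these temperature fluctuations for each incubator type will be calculated", and then "this measure will be used to consider whether the mOm incubator works as well as the standard one in maintaining temperature control".

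Section 8 also contains the following:

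- An expected size of fluctuation: "It is expected that these babies' temperatures will fluctuate by around one degree Celsius, and this is normal". It continues: "Thus, analysis will explore whether fluctuations for each baby keep within this bound".
- Normal limits of 36.5 to 37.5 °C for truncal skin temperature, given as an expectation.
- A promise that variations will be compared statistically between the two arms, with no estimand, test or criterion named.
- A statement of intent, "Although data analysis will be largely descriptive", in a sentence that goes on to say mOm's performance will be quantified statistically.
- A sample-size rationale: 36 babies give a two-sided 95% interval of ±0.33 °C around a mean fluctuation of about one degree.
- A statement that each baby is its own control.

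**The concern.** A claim that one device does as well as another concerns the difference between them. To support it, the plan needs an estimate of that difference with its uncertainty, and a statement of how large a difference would defeat the claim. Section 8 provides neither. It plans an interval for each incubator's own mean and leaves the reader to set the two side by side.

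Two things are at stake. First, the design is a cross-over, and its strength is that each baby is measured in both incubators. Separate intervals make no use of that pairing and do not measure how much more, or less, a baby fluctuates in mOm. Second, with no criterion fixed beforehand, the step from result to conclusion is a judgement made after the data are seen. The absence of an obvious difference could then be reported as evidence of similarity. This is the trial's main conclusion, and section 2 looks ahead to using the device where standard incubators are not available.

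**Working it through.** **1. Reproduce the plan's figure.** Inputs from section 8: n = 36, two-sided 95%, half-width 0.33 °C. No SD is given. The half-width of one mean is multiplier × SD / √n. With SD = 1:

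- normal: 1.960 × 1 / 6 = 0.327
- t, 35 df: 2.030 × 1 / 6 = 0.338

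Both round to about 0.33. Solving back, the implied SD is 0.33 × 6 / 1.960 = 1.01 (normal) or 0.33 × 6 / 2.030 = 0.98 (t). The stated precision therefore needs an SD of about 1 °C between babies, and it describes the mean of one incubator type.

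**2. Check whether the stated references limit the difference.** Suppose, for illustration, that mean fluctuation is 0.5 °C in the standard incubator and 1.0 °C in mOm. Both satisfy the one-degree reference. The difference is 1.0 − 0.5 = 0.5 °C and the ratio is 1.0 / 0.5 = 2, so fluctuation has doubled. Nothing in section 8 says whether that counts as doing as well. The limits of 36.5 to 37.5 °C also apply to each reading in each incubator, not to the contrast. Neither reference comes with a required proportion of babies or a consequence if it is missed.

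**3. Compare the separate intervals with the paired one.** With the same SD in both incubators and within-baby correlation ρ:

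SD of difference = SD × √(2(1 − ρ)); half-width = 2.030 × SD of difference / 6.

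The correlation is not in the documents, so a range is shown. SD 1.0 is the value the plan's precision implies. SD 0.5 is shown only for sensitivity.

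| ρ (assumed) | SD of difference, SD = 1.0 | Half-width, SD = 1.0 | Half-width, SD = 0.5 |
|---|---|---|---|
| 0.3 | 1.183 | 0.40 | 0.20 |
| 0.5 | 1.000 | 0.34 | 0.17 |
| 0.8 | 0.632 | 0.21 | 0.11 |

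At SD 1.0 each separate interval has half-width 0.34 (t) whatever ρ is. The interval for the difference runs from 0.40 down to 0.21 over the same rows, so the planned intervals do not reveal it. SD 0.5 does not fit the plan's own figure: it would give a single-mean half-width of 0.5 × 0.338 = 0.17, not 0.33.

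**4. What 36 babies could show if a margin were set.** Take a true difference of zero and require the upper limit of the two-sided 95% interval to lie below the margin. The smallest margin met with 80% power is about (1.960 + 0.842) × SD of difference / 6 (normal approximation). At SD 1.0:

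- ρ = 0.3: 2.802 × 1.183 / 6 = 0.55 °C
- ρ = 0.5: 2.802 × 1.000 / 6 = 0.47 °C
- ρ = 0.8: 2.802 × 0.632 / 6 = 0.30 °C

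**5. The measure itself.** Section 8 speaks of fluctuation in degrees and also offers the variance of temperature, which is in °C². A margin in °C cannot be applied until one per-baby summary is chosen.

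**The case against.** The strongest reply is that this is a mainly descriptive study. Section 3.1 sets out only to compare thermal care, 36 babies are justified by precision, and no formal non-inferiority or equivalence test is claimed. The plan is not without reference values either: it calls about one degree a bound, gives normal limits, promises a statistical comparison, and notes that each baby is its own control.

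Much of this stands. A descriptive aim is legitimate, and it is why rewording is an acceptable remedy. The reference values are real and should be acknowledged. But they are absolute, the one-degree bound is only to be explored, and none of them limits the difference. The promised comparison has no criterion, and section 5 uses arm for the order of the incubators, so that sentence does not by itself define a within-baby contrast. The similarity hypothesis in section 2 and the use of the intervals to judge it in section 8 remain.

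Two stronger readings are tempting, and the documents support neither. A reader might infer that no result could ever count against mOm. That goes too far: an mOm interval lying well above one degree would conflict with the plan's own bound. A reader might also infer that overlap of the two intervals is the success rule, and work out how large a difference could pass unnoticed. Section 8 says only that the measure will be used to consider the question. It names no overlap rule, so a figure built on one would not describe this plan.

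**Conclusion.** The concern holds in this form: absolute references exist, but the plan has no interval for the within-baby difference, no limit on that difference, and no rule connecting a result to the similarity claim. Followed as written, it can yield a similarity conclusion that the analysis does not support.

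The size of the problem can only be given as a range. It rests on an SD of about 1 °C, inferred from the stated ±0.33 °C, on equal SDs in the two incubators, and on assumed correlations of 0.3 to 0.8. On that basis 36 babies would estimate the paired difference to within about ±0.40 to ±0.21 °C. Whether that is precise enough cannot be judged without a margin. It would be wrong to conclude that 36 babies are too few, or that they are enough.

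**What to change.** In section 8, before any data are analysed:

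1. Define one per-baby, per-incubator fluctuation measure in °C.
2. Make the primary comparison the mean within-baby difference, mOm minus standard, with its two-sided 95% confidence interval. The per-incubator summaries can stay as description.
3. Choose one of the following:
   - **(a)** In sections 2 and 8, replace the similarity wording with a statement that the difference and its interval will be reported, and make no similarity claim.
   - **(b)** State a clinically justified margin, set by the sponsor and clinicians, and claim similarity only if the upper 95% limit lies below it. The margin should not be taken from 0.33 °C, which is the expected half-width of one incubator's mean and not a tolerance for a difference.

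Option (a) costs some wording and one paired analysis, with no extra babies. Its downside is the loss of the similarity claim. Option (b) keeps the claim available but means the trial can fail to meet it. It also requires stating the assumed SD and correlation and rechecking what 36 babies can show. At an SD of about 1 °C a tight margin may not be demonstrable with that number, so option (b) cannot be assumed to be free of extra recruitment.

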3.2 Secondary objectives

Assessment of:

- Comparability to maintain clinical stability by measurement of physiological parameters.
- The mOm incubators ability to maintain and regulate its temperature to within the appropriate BS standard⁵ in clinical practice.
- Comparison of between subject cleaning times.
- Incubator performance related adverse events.
- Staff feedback on the experience of using the mOm incubator (*i.e.* usability) will also be collected.

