4.2.2 Temperature stability and regulation

Hourly record of temperatures displayed on the incubator:

- the actual incubator temperature
- set temperature of the incubator
- Core/truncal temperature (from vital signs monitor/skin probe)

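### Read naturally, Section 8 summarises incubator temperature by its fluctuation, which does not answer whether the mOm incubator regulates to within the BS standard; no actual-minus-set measure is defined

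*Combined protocol and SAP*

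**What the plan says.** Section 3.2 lists as a secondary objective "The mOm incubators ability to maintain and regulate its temperature to within the appropriate BS standard", in clinical practice. Section 4.2.2 supplies the data under the line "Hourly record of temperatures displayed on the incubator". The entries include "the actual incubator temperature" and "set temperature of the incubator"; the third is the baby's core/truncal temperature. They are listed as separate readings, and no quantity is derived from them.

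For the analysis of secondary outcomes, Section 8 has one sentence: "Secondary outcome measures will be presented similarly". The text just before it describes the babies' temperatures. Besides graphs, it says that "summary statistics such as the variance of temperature throughout the two 24-hour periods will be presented", and then that "A 95% confidence interval for the size of these temperature fluctuations for each incubator type will be calculated".

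The documents nowhere define a difference between actual and set temperature, a numerical tolerance, a share of readings within tolerance, or how readings after a set-point change are handled. Section 6.2, Table 1, does provide an event log with start and end times for door and porthole openings.

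**The concern.** The objective is about accuracy: does the device hold its temperature within a limit? The statistics that Section 8 points to describe spread. Spread suits the primary outcome, where the question is how far a baby's temperature wanders. Applied to incubator temperature it has two faults.

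- **It ignores a steady gap.** An incubator that runs constantly above or below its setting has the same variance and range as one that runs exactly on it.
- **It counts deliberate changes.** If staff alter the setting, actual temperature should move. The variance of actual temperature then rises because the device did what was asked.

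At stake is the one objective that checks the device's temperature control against the cited standard in clinical use rather than on the bench. As planned, its result could look favourable for a device that is stable but off target, or unfavourable for one that followed its settings exactly.

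**Working it through.** **The plan's own figures.** The documents state no figure for incubator temperature. The precision figure for the primary outcome reproduces if the SD of fluctuation is taken as 1 °C, which is an assumption because Section 8 gives 1 °C as a mean: 1.96 × 1 / √36 = 0.327, against the stated 0.33 (0.338 with t on 35 df). The completeness rule, "19 of the 24, once-hourly temperature observations have been recorded for each incubator type", gives 19/24 = 79.2%, as stated. Neither figure is affected by this point.

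**Inputs.** There are 24 hourly readings per period (Section 8), with displayed actual and set temperature at each (Section 4.2.2). Step size, offset size and reading noise are not in the documents. They are assumed here and shown as ranges.

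**Steady gap.** Let actual = set + c at every hour. Adding a constant changes neither variance nor range: Var(x + c) = Var(x). For c of 0.5, 1 or 2 °C, the addition to the variance is 0.

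**Set-point step, perfectly followed.** If k of n readings are at one level and n − k are s °C away, the variance is s² × k(n − k) / [n(n − 1)]. For n = 24 and k = 12 this is s² × 144/552 = 0.261 s².

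| Step s (°C) | Variance | SD | Range |
|---|---|---|---|
| 0.5 | 0.065 | 0.255 | 0.5 |
| 1 | 0.261 | 0.511 | 1.0 |
| 2 | 1.043 | 1.022 | 2.0 |

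Mid-period is the largest case for a single step. A 1 °C step after 4 readings gives 4 × 20/552 = 0.145. With only 19 readings, split 10 and 9, a 1 °C step gives 90/342 = 0.263, so the minimum complete dataset behaves the same way.

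**With reading noise.** Simulated 24-hour periods with an assumed noise SD of 0.2 °C, 4,000 per scenario, gave:

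| Scenario | Variance of actual | Range of actual | Mean (actual − set) | RMS (actual − set) |
|---|---|---|---|---|
| On target, fixed setting | 0.04 | 0.78 | 0.00 | 0.20 |
| On target, 1 °C step at mid-period | 0.30 | 1.65 | 0.00 | 0.20 |
| Constant 1 °C shortfall | 0.04 | 0.78 | −1.00 | 1.02 |

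The step raises the variance 0.30/0.04 = 7.5-fold although control is unchanged. The shortfall matches perfect control on both variance and range. Actual minus set separates the cases correctly. The pattern is the same with noise SDs of 0.1 and 0.3 °C.

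**The case against.** The strongest reply is that Section 8 does not commit to a wrong measure. Its sentence on secondary outcomes is loose, and variance is offered only as an example of a summary statistic. A literal reading cannot hold for every secondary outcome: cleaning time, device events and a blood pressure that may be taken once a day have no useful within-period variance. This stands. Fluctuation is the natural reading for an hourly temperature series, not an explicit rule. The looser reading does not rescue the plan, though, because it leaves no measure specified for this objective.

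Set temperature is also a listed outcome. If it is graphed and summarised too, a step would appear in both series and could be recognised as deliberate, and graphs might show a gap. So a reader might infer that a steady gap is bound to go unnoticed, and the documents do not support that. What remains is that no combined plot is specified and that comparing two variances would not help: under a constant offset they are equal, as they would be under perfect control. A graph also gives no figure to hold against a standard.

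A reader might further infer that the plan will rank the two incubators in the wrong order. That is not supported either. The objective concerns the mOm device against a standard, whereas other bullets in Section 3.2 ask for comparisons. The Section 8 sentence that judges one incubator against the other concerns babies' temperatures.

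Finally, Section 4.2.2 covers stability as well as regulation, and a fluctuation summary does speak to stability. That is fair, but it leaves the regulation part unanswered. The documents also do not reproduce the BS limit, so whether it applies to hourly displayed readings in an occupied, frequently opened incubator has to be confirmed.

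**Conclusion.** The point holds as a mismatch between a secondary objective and the only analysis that the plan indicates for it. Variance and fluctuation size cannot show whether temperature is regulated to within a limit. They are blind to a steady offset of any size, and a single perfectly followed mid-period step of 0.5 to 2 °C inflates the variance by about 0.065 to 1.04.

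The direction follows from algebra and needs no assumption. The sizes rest on assumed steps, offsets and noise. The documents do not say how often settings change or whether offsets occur, so how much this would matter in the trial's data is unknown. The conclusion also rests on the natural reading of a loosely worded sentence.

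This is a gap in the analysis, not in data collection. It concerns one secondary objective in a largely descriptive analysis and does not touch the primary outcome or the 36 completed datasets. It is worth correcting before the data are analysed, because the choice of measure would otherwise be made with the results in view.

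**What to change.** In Section 8, define the measure for the incubator temperatures in Section 4.2.2 as displayed actual minus displayed set temperature at each hourly reading. Then:

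- For each baby and incubator type, report the mean deviation, the mean absolute deviation and the percentage of readings within the limit of the cited BS standard.
- Have the sponsor state that limit in the plan and confirm that it applies to displayed readings in an occupied incubator.
- Show separately the readings that follow a set-point change, visible in the hourly set record, or an opening logged under Table 1. State in advance how long after each event a reading counts as affected.
- Make the main result the mOm incubator against the standard, with the standard incubator shown descriptively alongside.
- Plot set and actual temperature on the same axes.

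The baby's core/truncal temperature, also listed in Section 4.2.2, can keep the primary outcome's treatment.

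The cost is revised analysis wording and a little more analysis work. No new data are needed, and neither the sample size nor the babies' care changes.

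### For hourly pulse, respiratory rate and oxygen saturation, section 8 names no estimate of a difference in level between incubators; the numerical summaries it does name cannot register a shift that lasts the whole 24 hours

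*Combined protocol and SAP*

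**What the plan says.** Section 3.2 makes comparability in maintaining clinical stability a secondary objective, and section 4.2.1 lists pulse rate, respiratory rate and oxygen saturation as hourly measures of it. Section 6.2 has them recorded throughout both periods.

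Their analysis rule in section 8 is one sentence: "Secondary outcome measures will be presented similarly". It follows the temperature analysis, which names:

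- graphical displays, and "summary statistics such as the variance of temperature throughout the two 24-hour periods will be presented";
- an interval for each incubator: "A 95% confidence interval for the size of these temperature fluctuations for each incubator type will be calculated";
- a focus stated as "Statistical analysis will focus on babies' temperature fluctuations whilst in each of the two incubators".

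Four other statements in section 8 bear on the point:

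- The plan describes its own character: "Although data analysis will be largely descriptive".
- For the temperature endpoint, after giving normal limits of 36.5 to 37.5 degrees, it says: "Variations from this endpoint will be analysed and compared statistically between the two arms of the study". No statistic is named.
- "Each patient will serve as their own control". No paired estimate or period term follows.
- "For continuous variables, such as weight, the mean, standard deviation, median and range will be presented". This sits in the paragraph on baseline factors.

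**The concern.** A variance, a range or any other measure of spread within a period is blind to where the readings are centred. If pulse ran several beats higher, or saturation a point lower, throughout the time in one incubator, each of these statistics would be the same as with no shift. Comparability of vital signs has two parts, steadiness and level. The named statistics address the first.

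They are also unsigned, and they are given incubator by incubator, so they leave unused the main advantage of a cross-over: each baby's two periods can be subtracted. What is at stake is whether a moderate, sustained difference in level would be estimated by a pre-specified method. The hourly values are kept, so means could be added later, but that choice would then be made after seeing the data.

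**Working it through.** **The plan's own figure.** Section 8 gives one precision statement: ±0.33 degrees with 36 babies. With a fluctuation SD of 1.0 degree (assumed; the plan gives only a mean of about one degree), 1.96 × 1.0 / √36 = 0.327, which rounds to 0.33. The figure reproduces, and it is a one-sample interval for one incubator. It says nothing about a paired difference or about vital signs.

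**Response of the named statistics to a shift.** Inputs: n = 24 hourly readings per period (sections 4.2.1 and 6.2) and an assumed step of size d lasting k of the 24 readings. If the step is uncorrelated with the baby's other fluctuation, the expected increase in within-period variance is d² × (k/n) × (1 − k/n) × n/(n − 1), and the mean moves by d × k/n.

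| k (hours) | Added variance, d = 6 bpm | Mean shift (bpm) | Added variance, d = 1 saturation point | Mean shift (points) |
|---|---|---|---|---|
| 2 | 2.87 | 0.5 | 0.08 | 0.08 |
| 12 | 9.39 | 3.0 | 0.26 | 0.50 |
| 22 | 2.87 | 5.5 | 0.08 | 0.92 |
| 24 | 0 | 6.0 | 0 | 1.00 |

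For example, at k = 2: 36 × (2/24) × (22/24) × (24/23) = 2.87. The zero at k = 24 is exact for every baby. The other rows are expected values, and one baby's variance can move either way. Changes of k and 24 − k hours add the same variance, and the sign of d drops out. The saturation columns hold away from the 100% ceiling.

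**What a paired estimate would give.** The documents give no SD for any vital sign, so all of these are assumptions: within-period pulse SD 10, hour-to-hour correlation 0.4 (AR(1)), baby-by-period SD P = 4, 6 or 8 bpm. The variance of a 24-reading mean is then v = (100/24) × 2.2407 = 9.34. For sequences of n1 and n2 babies,

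SE = √[ (P² + v)/2 × (1/n1 + 1/n2) ], half-width = t(34) × SE, with t(34) = 2.032.

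At 18/18 and P = 4: SE = √(25.34/2 × 0.1111) = 1.19, half-width 2.41 bpm. P = 6 and 8 give 3.23 and 4.10 bpm. For saturation (SD 2, v = 0.37; P = 0.5, 1.0, 1.5) the half-widths are 0.38, 0.56 and 0.78 points.

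**Detection, as illustration.** In simulated trials of 36 babies with a 24-hour pulse shift of 6 bpm, the adjusted difference excludes zero in about 82% to 99.9%; with 3 bpm, in about 30% to 70%. The formula agrees: shift/SE runs from 6/2.02 = 2.97 to 6/1.19 = 5.04, and from 1.49 to 2.52 at 3 bpm. Even a paired test on the within-period range flags 4.5% to 5.0% at 6 bpm, which is its false-positive rate. For a 2-hour change of 6 bpm the adjusted difference excludes zero in only 5% to 7%, so a mean cannot stand in for a measure of spread.

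**Why adjust for period.** Section 8 describes Excel random numbers and states no balancing. Under simple randomisation a 22/14 or more uneven split of 36 has probability 24%. At 22/14 an unadjusted mean difference carries (22 − 14)/36 = 22% of any period effect, or 0.89 bpm for an assumed 4 bpm effect. Adjustment removes this, and the 22/14 split itself raises the SE by 2.6% relative to 18/18 (2.47, 3.31 and 4.21 bpm for pulse).

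**The case against.** The strongest reply is that section 8 is not blind to level. It names graphical displays first, and plots of hourly readings would show both level and direction. Its list of statistics is open-ended, so means are allowed. For temperature it sets out normal limits before promising a comparison of variations, which can be read as departures from those limits. The word that carries the rule over to secondary outcomes is loose and may mean only descriptive displays by incubator. All of this stands. A reader might infer that the plan will omit level, or has no means of seeing it; the documents do not support that. They do show that no level estimate with its uncertainty is named for these signs. A graph supplies neither, the normal limits given are for temperature only, and the promised comparison names no statistic.

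A second reply is that the numbers lean on assumptions. That also stands. Nothing in the documents makes a sustained 6 bpm shift likely or clinically important, and halving it lowers detection considerably. Respiratory rate has no worked figure, and saturation has half-widths but no simulation.

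A third is that spread is a fair measure of stability, and that a difference without a comparability margin does not prove comparability. Both are right. Hence spread should stay, and the proposed interval is descriptive.

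**Conclusion.** The point holds as a gap in specification, of minor severity. For these three hourly signs the numerical statistics named by reference to temperature do not respond to a shift lasting the whole period and do not use the pairing, so the comparability objective in section 3.2 is only partly answered. That conclusion needs no assumed SD. The half-widths and detection rates rest entirely on assumed SDs, correlation and shift sizes and only indicate scale.

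A reader might go further and infer that safety is left unprotected or that the trial's main conclusion is at risk. The documents do not support either. Sections 2.1.2 and 5 let clinicians evaluate, move or withdraw a baby at any time, section 7.1 records events such as apnoea and bradycardia, and no success criterion rests on these outcomes.

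**What to change.** Add to section 8, before the data are analysed: for pulse rate, respiratory rate and oxygen saturation, each baby's 24-hour mean in each incubator will be calculated; the within-baby mOm-minus-standard difference will be reported with a 95% confidence interval from a linear model with incubator, period and baby; the number of readings per period will be shown; and within-period variance will be reported alongside as a summary of stability.

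The lowest saturation reading is best not added as a summary: it depends on how many readings were taken, and the 19-of-24 completeness rule covers temperature only.

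The cost is two or three sentences, a little more analysis and one degree of freedom for period. The readings are already collected hourly in both periods, so no new data item is needed.
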